3.3.3. Interruption or Discontinuation of Treatment

In accordance with legal requirements and ICH-GCP guidelines, every subject or his/her legal representative has the right to refuse further participation in the study at any time and without providing reasons (see also [Section 5.3](#)). A subject's participation is to be terminated

immediately upon his/her request. The Investigator should seek to obtain the reason and record this on the case report form (CRF).

If at the time of refusal a study product has already been administered, the subject should be advised on follow-up safety investigations. If a subject withdraws from the study, all efforts will be made to complete a final evaluation if possible. Subjects discontinued for having experienced an AE will be followed until the AE is resolved, a reasonable explanation is provided for the event, or the subject is referred to his/her own primary medical doctor (PMD). The specific AE in question will be recorded on the appropriate CRF.

If a subject develops a serious adverse event (SAE), his/her termination from the study will be considered by the Investigator. Similarly, if the subject develops conditions over the course of the study which would have excluded his/her entry in the study according to the safety-related medical exclusion criteria, he/she must be withdrawn immediately.

The subject may be withdrawn from the study at any time at the discretion of the Investigator for medical reasons and/or due to non-adherence to the treatment scheme and other duties stipulated in the study protocol. The reasons are to be documented on the CRF.

Individual patches may be discontinued if a reaction of a grade of 3 or greater (see [Section 3.5.5](#) for examples of values using additive grades from [Tables 3](#) and [Table 4](#)) occurs at any point during the study. Further patch applications of that product on that individual subject will be terminated. A “not patched” (NP) symbol and a score of 3 will be assigned for all subsequent days.

If a reaction is observed in any induction evaluation, a change in site location for the remaining applications in the Induction Phase will take place for that particular patch. See [Section 3.5.5](#) for interpretations of scores.

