test sites on Wednesday, Thursday, Friday, and Saturday), using the procedures described above for the Induction Phase. A possible follow-up reading may be conducted at 96 (± 4) hours for subjects with a score of 3 or higher at the 72 (± 4) hour time point.

Concomitant medications and AEs will be reviewed and recorded at the time of evaluation.

To be considered a **completed case**, a subject must have 9 applications of the study material and no fewer than 8 subsequent readings during Induction Phase and one application followed by 4 subsequent readings during the Challenge Phase. Only completed cases will be used to assess sensitization.

Rechallenge

A subject will be rechallenged to a specific study material if, in the opinion of the Investigator, any sign suggestive of contact sensitization (definite erythema with papules and/or edema) is observed at any of the 4 Challenge evaluations or at the Investigator's discretion for that study material.

Rechallenge patches will be applied at least 2 weeks after the end of the Challenge Phase. The study material will be applied to naïve sites on the back, in a manner similar to that used in the Challenge Phase. Rechallenge patches will remain in place for 48 (± 1) hour and patch sites will be evaluated 30 (+ 10) minutes and 24 (± 1), 48 (± 1), and 72 (± 4) hours after removal. As an example, patches will be applied on Monday and removed on Wednesday; the test sites will be evaluated on Wednesday, Thursday, Friday, and the following Saturday.

End of Study

At the EOS, all patches will be removed as described above, and the final evaluations of the test sites will be made.

An EOS examination will be conducted and consist of the following:

- Concomitant medication
- AEs
- UPT in females of childbearing potential

Concomitant medications and AEs will be reviewed and recorded during the whole study. For a detailed listing of scheduled study time points refer to the Visit Schedule and Assessments ([Table 2](#)).

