3.5.6. Criteria for Changing the Application Site or Conditions

A grade of 3 or higher to a study product (using [Table 3](#) and [Table 4](#)) observed at the first or second reading of the Induction Phase would indicate the subject to be pre-sensitized, and application of the product in question would be discontinued.

After the second reading of the Induction Phase, reactions graded 3 or higher (using [Table 3](#) or [Table 4](#)) require that the investigational product be applied to a naïve site under occlusive conditions. Such a change of application site may occur no more than twice during the Induction Phase for a particular product, after which applications of the product will be discontinued for that subject for the remainder of the study. Subjects requiring site changes due to irritancy in the Induction Phase will be considered evaluable for sensitization, provided that they receive a total of no fewer than 9 applications of the product.

No more than 2 changes for a given product will occur, whether the changes are to a new site under occlusive conditions (first move) or a new site under semi-occlusive conditions (second move).

Occlusive patch conditions include a Webril® cotton patch surrounded with Blenderm tape and covered with paper tape. There is no air flow under the patch. Semi-occlusive patch conditions include a Webril® cotton patch covered with paper tape, to allow air flow under the patch itself.

The 3-week period of continuous patch contact during the Induction Phase frequently results in tape-related irritation that is exacerbated by warm weather, but which occurs among some individuals irrespective of the season. Since adhesive tape is an integral part of the test article, tape-related irritation at the site will be documented as an application site reaction using the symbol “T” from [Table 5](#). Severe tape-related irritation will require a change of application site. Mild and moderate tape related reactions will not require of a change of application site. If all sites are experiencing tape reactions, the patch sites will be discontinued and a not patched (NP) symbol will be recorded for the remainder of the study. The subject will be discontinued from the study. An AE will be recorded in order to follow through to resolution of the tape related reaction.

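### Sensitization is assessed only in completed cases, so a subject whose product is stopped in late Induction because of strong reactions drops out of the primary assessment with no rule to keep the reaction in view

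*Combined protocol and SAP*

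**What the plan says.** **Who is assessed.** Section 3.5.1 restricts the primary assessment: "Only completed cases will be used to assess sensitization". To qualify, "a subject must have 9 applications of the study material and no fewer than 8 subsequent readings during Induction Phase", plus one Challenge application with four readings. Section 4.3 is looser and takes everyone who completes Challenge. Neither makes an exception for a product stopped because of a reaction. Section 3.3.1 enrols until 200 completed subjects are available.

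**When a product is stopped.**
- Readings 1 and 2 (3.5.1, 3.5.6): a grade of 3 or more is taken as pre-sensitization and the product is stopped.
- After reading 2 (3.5.6): such a reaction moves the patch to a naive site. Two moves are allowed, "after which applications of the product will be discontinued for that subject for the remainder of the study". Subjects who were moved stay evaluable if they still receive 9 applications.
- Any time (3.3.3): "Individual patches may be discontinued if a reaction of a grade of 3 or greater" is seen, and then "Further patch applications of that product on that individual subject will be terminated".

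**What happens to the reaction.** For irritancy, 3.3.3 has a rule: a not-patched "symbol and a score of 3 will be assigned for all subsequent days", and 4.6.1 carries the 3 forward. For sensitization there is no counterpart. Section 3.6.1 keeps responses that can be graded on Tables 3 and 4 out of the adverse events. The narrative in 4.6.2 covers Challenge and Rechallenge reactions, not Induction stops.

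**What counts as a case.** The explicit criterion in 4.6.2 is recurrence at Rechallenge of a Table 3 response of 3 or more, at least as severe as at Challenge. Sections 4.1 and 4.6.2 say that one such subject suggests the product may cause hypersensitivity.

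**The concern.** Membership of the assessed set can depend on the outcome being assessed. A subject who reacts at grade 3 or more on successive sites late in Induction is, if anything, more likely than others to be sensitized. The plan removes that subject from the sensitization assessment of that product and lets another completer make up the 200. The reaction then shows at most as an irritation score.

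A single case carries the conclusion here, so a report of no sensitization in 200 could coexist with a persistent reactor whom the sensitization results never mention. The bound in section 4.2 assumes that reactors are as likely to stay in the assessed set as everyone else.

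**Working it through.** **1. The plan's own figure.** Section 4.2 gives a 95% upper bound of 1.5% for no cases in 200. The exact one-sided bound is 1 − 0.05^(1/200) = 1.487%, and the rule of three gives 3/200 = 1.50%. The two-sided version, 1 − 0.025^(1/200) = 1.83%, does not match. The stated figure is therefore correct as a one-sided bound; the issue is who is in the 200.

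**2. Can a stopped subject be a completed case for that product?** Reading k follows removal of patch k, so a stop at reading k means k applications received.

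| Stop at Induction reading | Applications received | Challenge patch | Completed case? |
|---|---|---|---|
| 3 to 8 | 3 to 8, below 9 | none | no |
| 9 | 9 | none | no |

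**3. Earliest required stop under 3.5.6.** Grade 3 or more at reading 3 gives the first move, at reading 4 the second move, and at reading 5 no move is left. The product is stopped after 5 applications. Under the permissive sentence in 3.3.3, one reaction at reading 3 would be enough.

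**4. Effect of one such subject.** The exact one-sided upper bound for x cases in N (x below N) is the 0.95 quantile of Beta(x + 1, N − x).

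| Situation | x/N | Rate | Upper bound |
|---|---|---|---|
| Stopped reactor left out, 200 other completers | 0/200 | 0% | 1.49% |
| The same subject kept and counted | 1/201 | 0.50% | 2.34% |

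The second row only illustrates size. Adding a non-completer because that person reacted selects on outcome, so 2.34% does not have nominal 95% coverage.

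**5. Challenge reactor who is not rechallenged.** This subject already meets the completed-case rule and stays among the 200. Counted as a case, the result is 1/200 with a bound of 2.35%; not counted, it is 0/200 with 1.49%. No stated rule chooses between them.

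**6. What cannot be computed.** The documents give no rate of product stops, of withdrawals for reactions, or of missed Rechallenges. The chance that a true case is lost is therefore not estimated.

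**The case against.** The strongest reply is that a Challenge on naive skin is how this design separates allergy from irritation. Section 3.1 rests interpretation on the Challenge response together with the Induction pattern, and 3.5.6 attributes site changes to irritancy. A subject who was never challenged has no confirmed endpoint. That stands, and it is why the completed-case analysis should remain primary. It does not justify leaving the subject out of the sensitization results altogether.

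Four stronger readings are tempting, but the documents do not support them.

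- *Induction reactors are generally lost.* After reading 2 the rule is to move the patch, and moved subjects remain evaluable with 9 applications. Section 3.3.3 only permits a stop, and it also calls for a site change after an Induction reaction. Its permissive sentence and the example in 3.5.5.1, where a combined score of 3 ends patching at that site, leave some ambiguity, but most reactors are kept. Stops at readings 1 and 2 are labelled pre-sensitization, which is separate from the induced sensitization in section 2.
- *A suspected allergy forces withdrawal.* One sentence in 3.3.3 says that a subject who develops an excluding condition, "according to the safety-related medical exclusion criteria, he/she must be withdrawn immediately". It does not name test-site reactions. The general provision is discretionary: "The subject may be withdrawn from the study at any time at the discretion of the Investigator for medical reasons". Challenge readings begin after the patch is off and last 72 hours, and all efforts are to be made to obtain a final evaluation, so loss in that window is speculative.
- *A Challenge reactor who is not rechallenged becomes a non-case.* That subject stays in the 200 and receives a narrative and the Investigator's opinion. Section 4.6.2 also says confirmation applies where necessary. The status is undefined, not negative.
- *One case proves sensitization.* The wording is that one case suggests a potential.

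Two further points have some force. Section 4.6.2 plans no rate or interval, so the shift in the bound bears on the precision claim in 4.2; what matters for the conclusion is none versus one. Section 4.1 also announces a SAP, and a rule might be placed there. No SAP text is among the supplied documents, and the restriction is written in the protocol that the SAP is meant to supplement.

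**Conclusion.** The concern holds in a narrow form. Section 3.5.1 excludes, because of the reaction itself, a subject whose product is stopped after Induction reading 2 for grade 3 or higher responses. The plan offers no other sensitization output in which that subject would appear. One such subject separates 0/200 with a bound of 1.49% from 1/201 with 2.34%, and separates a clean result from one that sections 4.1 and 4.6.2 would treat as a signal if the case were confirmed.

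This rests on reading the completed-case rule as applying to each material, as its wording indicates, and on no rule to the contrary in the SAP that was not supplied. The frequency is unknown and may be low, because site changes retain most reactors. The unrechallenged Challenge reactor is a smaller matter: a missing classification, not an exclusion.

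**What to change.** Keep confirmed cases among completed cases as the primary analysis, unchanged. In sections 3.5.1, 4.3 and 4.6.2, add the following.

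1. **Class.** Any subject stopped on a material, or withdrawn, after Induction reading 2 because of a Table 3 reaction of grade 3 or more to it is classed by the blinded Investigator as suspected, unconfirmed. A Challenge reactor who is not rechallenged goes in the same class.
2. **Reporting.** List each such subject with a narrative, by material, including vehicle and saline. List stops at readings 1 and 2 separately as pre-sensitized, outside both counts.
3. **Sensitivity analysis.** Count confirmed plus suspected cases as a worst case. Use as denominator all subjects who received the material beyond Induction reading 2, noting that those who left before Challenge without reacting were never challenged. Alternatively, present the worst-case count without claiming nominal 95% coverage. Do not add only reactors to the completers and attach an ordinary 95% bound.
4. **Conclusion.** A statement of no sensitization should require no suspected, unconfirmed case on CCP-020, or should report and discuss any such case.

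The cost is a few sentences, one extra class, one summary row and one listing, with no added subjects, visits or patches. The downside is that some irritant reactions will be carried as suspected, so the worst-case figure will look less favourable. The vehicle and saline results, reported in the same way, help the reader judge that.

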3.2. Discussion of Design

Allergic contact dermatitis (ACD), also referred to as dermal sensitization, is a delayed-type hypersensitivity reaction induced by small reactive chemicals (haptens).² It is a T-cell-mediated skin inflammatory systemic reaction, caused by repeated skin exposure to contact allergens. Erythema, edema, and occasionally papules and vesicles characterize the clinical appearance of this reaction. The ACD inflammatory skin reaction occurs as a delayed response (24-48 hours or longer) after contact with a sensitizing chemical.

In pharmaceutical and cosmetic industries it is mandatory to identify chemicals that are potential ACD inducers before they become a part of a new product.² Substances that come into contact with human skin need to be evaluated for their propensity to irritate and/or sensitize. Once an appropriate pre-clinical safety evaluation has been performed, a reproducible, standardized, quantitative patch evaluation procedure must be used to demonstrate that a particular material can be applied safely to human skin without significant risk of adverse reactions.³

Repeated insult patch test (RIPT) evaluation is a predictive patch study that can detect weak sensitizers that require multiple applications to induce a T-cell-mediated (Type IV) immune response sufficient to cause an allergic reaction. Irritant reactions may also be detected using this evaluation method, although this is not the primary purpose of this procedure.

The human RIPT study design is based on the Modified Draize procedure, and is an accepted standard methodology used for assessment of skin sensitization.^{4,5}

The IPs in the study will be CCP-020 (Diacerein 1%) topical ointment and Vehicle. The negative irritant control field will be 0.9% saline, 0.2 mL, applied topically under occlusive conditions.

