3.4.5. Assignment to Treatment

3.4.5.1. Randomization

Each subject who signs an informed consent form (ICF) will be assigned a screening number. If the subject meets all of the inclusion and none of the exclusion criteria, and successfully completes the screening procedures, they will be enrolled in the study. Upon enrollment, each subject will be assigned a unique subject number and receive a randomization code, indicating application placement of the study materials. Each subject in this study will serve as his or her own control. All subjects will receive the IPs and control products at adjacent application sites.

The IPs (CCP-020 [Diacerein 1%] topical ointment and vehicle) and study control (saline) will be assigned in a randomized sequence to test Sites 1 through 3 using a set of independent 3-by-3 Latin squares. The same study material will be applied to the same test site throughout the study.

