Subjects who are absent once during the 3-week, 9-patch Induction Phase will be instructed to keep the patches in place and return to the facility on their next scheduled visit. They will be scheduled to receive a make-up (MU) patch application at the last Induction visit. The MU patches will be removed 48 – 72 (\pm 4) hours later and the sites will be graded. If subjects fail to return for removal/evaluation of the MU patch, a no ninth grading (N9G) will be recorded.

In cases where the subject misses the 9th evaluation in Induction Phase, the subject will be allowed to remove the patches by themselves in accordance with investigative personnel instructions. A telephone log will be written for any subjects that experience this situation to document the telephone conversation regarding the removal by subject.

Subjects who miss the 9th evaluation, but have had 9 patch applications will be considered to have completed the Induction Phase.

During Induction, the actual patch test grade is a combination of a numerical ([Table 3](#)) and letter ([Table 4](#)) grade consistent with the definitions given in the grading scales. A grade of 3 or higher to a specific study material (see [Section 3.5.5](#) for interpretation of symbols) observed at the first or second reading of the Induction Phase would indicate the subject is pre-sensitized, and application of the product(s) in question would be discontinued. If these reactions are observed after the first or second reading of the Induction Phase, this would necessitate a change in patch location to a naïve site. A second site change to the specific study material would potentially require a patch condition change to semi-occlusive conditions for the remaining applications in the Induction Phase (see [Section 3.5.6](#)).

Rest Period

During the Rest Period of approximately 10-14 days, subjects will not receive any application of study materials.

Challenge

At the Challenge Phase, subjects who have completed the Induction Phase and the Rest Period will have identical patches applied to naïve sites. Patches will remain on the naïve sites for 48 (\pm 1) hour to be evaluated at 30 (+ 10) minutes and 24 (\pm 1), 48 (\pm 1), and 72 (\pm 4) hours following patch removal (e.g., apply patch on Monday, remove patch on Wednesday, evaluate

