4.2. Sample Size and Power Considerations

The sample size of 200 evaluable subjects conforms to industry and regulatory standards for determination of dermal sensitization potential. In the absence of any sensitization reactions, a 95% upper confidence bound on the population rate of sensitization would be 1.5%.

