4.6.2. Analysis of Dermal Sensitization Potential

The determination of dermal sensitization potential will be based on specific scoring criteria ([Table 3](#)) derived from observations in the Challenge Phase of the study and confirmed in the Rechallenge Phase, if necessary.

Criteria specified in [Section 3.5.5](#) may cause the continuation of a subject into the Rechallenge Phase of the study. The recurrence of a cutaneous response of 3 or greater from [Table 3](#) at Rechallenge equivalent to or more severe than that observed at Challenge will be considered indicative of a sensitization reaction. The observation of such a response in even a single subject suggests that the test product may have the potential to cause hypersensitivity.

A narrative description of reactions in the Challenge and Rechallenge Phases will be provided together with the opinion of the Investigator as to whether such reactions are felt to be indicative of contact sensitization.

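### Rechallenge, as most naturally read, re-applies only the material that reacted, and the rule that decides sensitization makes no comparison with concurrent vehicle or saline sites

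*Combined protocol and SAP*

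**What the plan says.** The trial compares CCP-020 ointment, its vehicle and saline within each subject. Section 3.4.5.1 puts it this way: "Each subject in this study will serve as his or her own control". A set of three patches is described for Induction and for Challenge. At Challenge, "subjects who have completed the Induction Phase and the Rest Period will have identical patches applied to naïve sites".

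Rechallenge is worded differently. Section 3.5.1 states: "A subject will be rechallenged to a specific study material if, in the opinion of the Investigator, any sign suggestive of contact sensitization" is seen at any of the four Challenge readings, or if the Investigator so decides for that material. On procedure it says: "The study material will be applied to naïve sites on the back, in a manner similar to that used in the Challenge Phase". Rechallenge starts at least two weeks after Challenge ends and uses the same 48-hour application and the same four reading times.

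Section 4.6.2 bases the determination on Challenge, confirmed at Rechallenge where needed. The recurrence of a Table 3 response of 3 or greater "at Rechallenge equivalent to or more severe than that observed at Challenge will be considered indicative of a sensitization reaction". Sections 4.1 and 4.6.2 add that one such subject is enough to suggest that the product may cause hypersensitivity. A narrative and the Investigator's opinion accompany the result.

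On size, Section 4.2 says: "The sample size of 200 evaluable subjects conforms to industry and regulatory standards for determination of dermal sensitization potential". With no reactions, "a 95% upper confidence bound on the population rate of sensitization would be 1.5" percent.

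**The concern.** The step that confirms or refutes sensitization, which is the primary objective, appears to drop the within-subject control on which the rest of the design relies. The protocol expects non-allergic reactions. Section 3.2 notes: "Irritant reactions may also be detected using this evaluation method, although this is not the primary purpose of this procedure". Section 3.5.6 keeps subjects whose patches were moved for irritancy in the sensitization assessment, provided that they receive nine applications. If such a subject reacts at Challenge for a reason that is not allergy, the same 48-hour patch may well produce the same reaction again, and recurrence is what the rule counts.

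Two things are at stake. A reaction caused by occlusion, or by skin that is generally reactive at that time, could be recorded as sensitization to CCP-020. A reaction to an ingredient of the base could be recorded without being attributed to the base.

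There is also a grading issue. If one patch is applied, the evaluator knows that it is the material that reacted before, and must then grade a response whose severity is compared with the earlier one. That invites expectation bias.

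**Working it through.** **1. What is applied in each phase**

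| Phase | Materials | Source |
|---|---|---|
| Induction | CCP-020, vehicle, saline | 3.4.5.1, 3.5.1 |
| Challenge | CCP-020, vehicle, saline | 3.5.1 |
| Rechallenge | the specific material that reacted; no concurrent control required | 3.5.1 |

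Sections 3.4.1 and 3.5.1 describe control patches for Induction and Challenge only. Table 2 marks applications at Rechallenge but does not say of what.

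**2. What the rule uses.** Section 4.6.2 has two conditions: a Table 3 grade of 3 or more at Rechallenge, and severity at least equal to that at Challenge. Neither refers to the vehicle or saline grade, at Rechallenge or at Challenge.

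**3. How old the existing control readings are at Rechallenge**
- Challenge readings: at least 14 days, counted from the end of Challenge (3.5.1).
- Last Induction reading: about 10 days of rest (the lower end of 10 to 14) + 2 days of patch + 3 days to the 72-hour reading + 14 days = about 29 days or more.

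A vehicle site that reacted only weakly at Challenge, for example grade 1, need not meet the Rechallenge trigger. It would then have no reading at the second time point.

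**4. What concurrent controls would show**

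| Cause of a repeat CCP-020 reaction | Vehicle | Saline | Distinguished from diacerein allergy? |
|---|---|---|---|
| Diacerein allergy | clear | clear | reference case |
| Irritancy of diacerein itself | clear | clear | no |
| Reaction to the base | reacts | clear | yes |
| Occlusion or generally reactive skin | reacts | reacts | yes |

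These are idealized patterns. They show which causes the control patches address and which they do not.

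**5. The plan's figure, reproduced.** Inputs from Section 4.2: n = 200 and no reactions.
- Exact one-sided bound: 1 − 0.05^(1/200) = 1.487%.
- Rule of three: 3/200 = 1.500%.
- Two-sided version: 1 − 0.025^(1/200) = 1.828%, which does not match.

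The stated 1.5% is therefore right as a one-sided bound.

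**6. Effect of one misclassified subject.** The rate becomes 1/200 = 0.5%. The one-sided exact bound solves (1 − p)^200 + 200·p·(1 − p)^199 = 0.05, which gives p = 2.35%. The bound moves from 1.49% to 2.35%, and the single-subject conclusion is triggered.

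**7. Sensitivity to an assumed rate.** Let q be the chance that a subject shows a recurrent grade of 3 or more that is not allergy to diacerein. The documents give no value for q. The chance of at least one such subject is 1 − (1 − q)^200:

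| Assumed q | At least one in 200 |
|---|---|
| 0.05% | 9.5% |
| 0.1% | 18.1% |
| 0.25% | 39.4% |
| 0.5% | 63.3% |
| 1% | 86.6% |

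This shows only how sensitive a one-subject rule is to a rare event. It does not estimate how often the event occurs, nor how much the fix would remove, because q includes irritancy of diacerein and reactions to the base.

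**The case against.** The other side has several good arguments, and part of each stands.

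- **The text does not exclude controls.** Section 3.5.1 never says that only the reacting material is applied. It refers to patches and sites in the plural and to a procedure similar to Challenge, where three patches are used. A full set is therefore possible. But the repeated reference to one specific material makes single-material application the more natural reading, and no sentence requires the controls.
- **Controlled evidence already exists.** A reader might infer that the trial has no means of telling allergy from a vehicle or occlusion reaction. The documents do not support that. All three materials are read four times at Challenge and are scheduled for nine readings in Induction. Section 3.1 uses both phases for interpretation. A CCP-020 reaction with clear vehicle and saline sites at Challenge already argues against the base and against occlusion, and a control site that reacted strongly could itself be rechallenged. What remains is that this evidence is older and does not enter the stated rule.
- **The blind.** A reader might infer that blinding breaks down at Rechallenge. A lone patch reveals which material reacted, not whether it is CCP-020, vehicle or saline. Section 3.4.5.2 already concedes that complete blinding cannot be assured. The weakness is expectation.
- **Filters apply.** Entry to Rechallenge depends on the Investigator's judgement, the response must be at least as severe as before, the Investigator's opinion is reported, and the conclusion is worded cautiously. These filters reduce misclassification, but none of them is a comparison with a control.
- **Allergy to the base still counts.** The objective in Section 2 concerns the ointment. A reaction to one of its ingredients is therefore not a false positive for the product. Only attribution to diacerein is lost.

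**Conclusion.** The point holds as a cheap improvement to the confirmatory step. On the natural reading of Section 3.5.1, Rechallenge has no concurrent control. On any reading, the rule in Section 4.6.2 makes no comparison with vehicle or saline. Because one subject suffices for a positive conclusion, one misclassified reaction changes the result from 0/200 to 1/200 and the upper bound from 1.49% to 2.35%.

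The conclusion rests on two assumptions: that Rechallenge is carried out as its wording suggests, and that some non-allergic reactions recur. The documents give no frequency for the second, so the probability of a wrong conclusion cannot be stated. The planned sample size and the 1.5% bound are not in dispute. Concurrent controls would address the base, occlusion and general skin reactivity. They would not separate irritancy of diacerein from allergy to it. That distinction still depends on the Induction pattern, the time course and the Investigator's judgement.

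**What to change.** - **Section 3.5.1, Rechallenge.** State which materials are applied. When CCP-020 is rechallenged, apply vehicle and saline patches alongside it at naïve sites, in a re-randomized order, graded by the blinded evaluator. Re-randomizing matters because, with the original order, the evaluator could tell from the position which site had reacted.
- **Sections 3.4.5.1 and 3.5.1.** Add an exception for Rechallenge to the rules that each material keeps its test site and that the site numbering stays fixed.
- **Section 4.6.2.** Report each Challenge and Rechallenge reaction by pattern: CCP-020 only, CCP-020 and vehicle, or all sites. Do not count an all-sites pattern as sensitization to CCP-020 on the grade rule alone. A CCP-020 and vehicle pattern would still count for the ointment, but could be attributed to the base.

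**Cost.** Two extra patches in each subject rechallenged to CCP-020, at visits already planned, with slightly more patch exposure for those subjects. The change needs a protocol amendment, which may require IRB review under Section 5.5.1. The proposal covers Rechallenge to CCP-020 only, so it does not add CCP-020 exposure for a subject who reacted only to vehicle or saline. The sample size and the zero-event bound do not change.
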